## C2. EHR-CHW Intervention

The implementation and content of EHR and CHW components of the intervention at each clinic align with the Chronic Care Model.

**EHR Components:** This component of the intervention will leverage clinical information systems and impact delivery system design by enhancing practice capacity and workflow to implement and use EHR-based alerts to identify patients with uncontrolled diabetes. The EHR component of the integrated EHR-CHW intervention will include: 1) An alert to identify South Asian patients with uncontrolled diabetes Hb1AC >7 and 2) Generation of registry lists of individuals with A1C >7). Building upon existing protocols the study team will coordinate the implementation of the proposed EHR modifications at clinics. The implementation process will be characterized by: 1) Workflow analysis; 2) Procedures for identifying system requirements; and 3) Adequate training and support for users upon and following go-live.

*Workflow analysis.* Using a rapid assessment process, baseline workflow analysis will be conducted at each clinic. The workflow analysis consists of an iterative process including ethnographic observation and key informant interviews (see below) to provide contextual data on organizational workflow, culture, and practice. Results from the analysis will be used to improve alert and registry functions and to align with the workflow of each clinic.

*Implementation of System Requirements for the Intervention.* System requirement definition and implementation ensures that various EHR systems across PCP clinics are configured to provide the functionality called for by the study design. The research team will work with a PCP clinics to develop a framework for creating the proposed EHR enhancements. This process includes specifying and confirming the system's functional requirements based on the users' needs as well as the study design. The EHR modifications will be made at each study clinic, and providers and staff will be trained. Functional and technical specifications (and any updates) will be maintained and documented for training, workflow development, troubleshooting and dissemination purposes.

*Training.* The training will be designed to enable clinicians to use the decision-supports and/or alerts independently, proficiently, and effectively. At the start of the intervention period, clinicians will receive an estimated 8 hours of didactic and interactive training. Individualized training will also be available during the initial implementation period for all users. Clinic staff will also be provided with user documentation.

### **CHW Component:**

*CHW Protocol.* Patients that meet the eligibility criteria will be drawn from registry lists and randomized to treatment or waitlisted control.

#### *1. Data collection and consenting with treatment participants*

Patients assigned to the treatment group will be sent an invitation letter to participate in the CHW intervention (See *Recruitment Letter for CHW Intervention*). Invitation letters will be followed up with phone calls by CHWs (See *Script for Telephone Screening for CHW Intervention*). In addition, a screening form (See *Telephone Screening Form for CHW Intervention*) will be completed to verify eligibility. CHWs will call patients a maximum of 10 times over a two-week period at varying times of day to screen and invite them to enroll into the study.

The CHW intervention includes a protocol that consists of 5 monthly 90-minute group health education sessions, providing the tools and strategies to manage diabetes. All sessions employ adult learning techniques and group-based learning and activities. All session materials have been culturally and

linguistically adapted into Bengali, Urdu, Hindi, Punjabi, and Nepali. Sessions will be held remotely via audio phone calls via telephone, MCIT approved Zoom or Webex platforms, remote sessions will be conducted for the community health worker intervention as a result of the current COVID-19 pandemic. Remote sessions are preferred due to limited ability to properly socially distance in the small offices of the participating PCP clinics and community organizations. When clinic restrictions and limitations due to COVID-19 have been lifted, a modification to the protocol will be submitted and in person health education sessions will resume as initially underlined in the protocol. In that circumstance sessions will be implemented in PCP clinics and, community spaces identified by partner agencies or at private residences with approval from tenants.

Patients will also receive 2 one-on-one phone calls from CHWs to discuss individualized challenges, strategies, and action plans for diabetes management and referral to community resources. The tested curriculum also incorporates a family-centered approach; for example, family members are invited to attend sessions and participate in one-on-one calls.

In addition to group sessions, patients will receive up to 9 follow-up phone calls from CHWs, during which individualized challenges, strategies, and action plans for improving diet and physical activity will be discussed (See *Progress Note Form for CHW Intervention*). CHWs will also contact patients via text messages to communicate study activities via a secure NYULMC phone.. CHWs will also work with partner agencies to conduct community-level activities, such as culturally tailored physical fitness classes and healthy cooking demonstrations, that patients will be invited to attend. The CHWs will make necessary referrals to other services available in the community (i.e. exercise classes, social services, mental health, tobacco cessation, etc.). Participants will also complete the *Mobile Phone Use Questionnaire* to assess the type of phone they use, use of messaging and data capabilities on the phone after the first session. This questionnaire will be used to allow the CHWs to communicate with the participant according to their preferences and to tailor future interventions. CHWs will complete an *Encounter Report* to document unscheduled encounters with study participants (ie. such as when a participant calls the CHW to request referrals to services or to report an illness or diabetes related event or new diagnosis.) In order to understand the COVID-related impact and needs of study participants in managing their health and to improve CHW referrals during the COVID19 pandemic, CHWs will complete a Rapid COVID Assessment via phone up to once per month or as needed (see study forms for: *Rapid COVID Assessment*, *Rapid COVID Assessment – Repeating Form*).

Multiple sessions will be hosted at varying times/days of the week to accommodate schedules of both working individuals and at-home caretakers. Small incentives will be provided throughout the intervention to encourage ongoing attendance, and incentives will be distributed at program completion for individuals who attended all 5 sessions.

Verbal consent (See application for *Waiver of Authorization and Documentation of Consent*) will be obtained via telephone. A verbal consent is preferable due to the 1) remote nature of the intervention 2) the South Asian immigrants have limited technological literacy and are unable to complete an electronic consent via REDCap as this will also require them to have email accounts which are used sparingly in this population.

Upon completion of the verbal consent, CHW will offer to provide a key information page (see *Key Information (Patients)*), this form contains all the elements of consent and can be provided via text upon participant agreement. Clinical measures related to diabetes (e.g., HbA1c, BMI) will be obtained from regularly generated diabetes registry lists that practices generate as part of quality improvement initiatives and these measures will be tracked over time. In addition, baseline surveys will also be conducted by NYU study staff within two weeks after consent. (See *Patient Baseline Survey for CHW Intervention*). (See *CHW Participant Baseline Survey in English and Bengali*). An Urdu baseline survey will be

submitted for approval in a subsequent modification as translation is in progress. A follow-up survey will be completed with treatment participants approximately six months after the start of intervention in order to evaluate the effectiveness of the CHW intervention. Survey questions include health access, socioeconomic status, personal and family history of Type II diabetes and its risk factors. Measures will be drawn from nationally validated surveys such as the BRFSS survey. Translated Bengali and Urdu follow-up surveys will be submitted in a subsequent modification.

- Self-efficacy: whether participants feel that they can successfully or competently complete the task of seeking screening or prevention services for diabetes and engage in self-management of diabetes. Measures will be drawn from the Personal Mastery Scale, the Rosenberg Self-Esteem Scale (1965), and the Bandura Self-Efficacy Scale.
- Social Support: number of friends and family members in participants' social network, type of support received (e.g., enabling, tangible, emotional support), the density and degree of homogeneity of their social network, the use of faith-based organizations or religious counselors for support. Measures will be drawn from the Arizona Social Support Interview Schedule (Barrera 1980, 1981) and the UCLA Social Support Interview
- Spousal Support: the degree and nature to which participants receive support and encouragement from spouses or partners to initiate and/or maintain screening and prevention services. Measures will be drawn from Multi-dimensional Scale of Perceived Support.
- Knowledge and Health Behaviors:
- Perceived severity – i.e., diabetes can lead to heart attacks and strokes
- Perceived susceptibility – i.e., untreated diabetes can lead to renal complications
- Perceived benefits – i.e., engaging in self-monitoring will reduce the risks of diabetes
- Perceived barriers – i.e., negative side effects are worth enduring (i.e., barriers do not outweigh benefits)
- Diabetes risk factors: We will include questions on the importance of self-monitoring, nutrition and diet, smoking habits, and exercise patterns.
- COVID-19 Pandemic: Participants enrolled during the COVID-19 pandemic will be asked questions on vaccine hesitancy and COVID19 vaccination; as well as questions on mental health and mobile/technology use in order to understand how participants' chronic health and mental was affected in during the pandemic and to understand how best to tailor remote intervention strategies to encourage vaccination among patients with diabetes who are at higher risk for complications from COVID-19.

Surveys will take approximately 30 minutes to complete.

## *2. Data collection and consenting with waitlisted control participants*

The NYU study team will only be collecting de-identified EHR data with control participants (n=443). EHR data will include clinical measures related to diabetes (e.g., HbA1c, BMI) and will be obtained from regularly generated diabetes registry lists that practices generate as part of quality improvement initiatives and these measures will be tracked over time. The PCPs will be conducting the de-identification and the link to the unique identifier will remain with the PCP staff. NYU study team members will not have access to these links. Beyond EHR data collection, no other data collection will occur with control participants (e.g., no survey data collection) and the control group will not have any interaction with study personnel for the purposes of research. PCPs will invite control participants to CHW education sessions at a later time (post round 1 of CHW intervention with treatment participants) as a point of service (i.e., not for research

purposes). The PCPs themselves are not involved in the research aside from providing NYU with de-identified EHR data.

#### C3. Care Coordination Component

The intervention will support team-based care by creating structured mechanisms for feedback between PCPs and CHWs and increasing care coordination that includes three components, adapted from best practices noted in other studies. First, templates will be created that CHWs can complete - Providers will be given access to these templates which will include: 1) CHW action planning documents and individualized counseling conducted during phone calls; and 2) Patient progress in reaching goals related to diabetes management. Second, health coaching and referral materials are available to providers through the EHR, including 1) Culturally adapted CHW curriculum materials; and 2) Systems to link patient to community resources and activities. Healthify's tools, as described above, will be used to facilitate these feedback mechanisms. Third, CHW communication with the healthcare team will be facilitated by participation and report-backs from CHWs. Frequency of participation will be clinic-specific and guided by input from the provider and workflow analysis findings to avoid provider burnout.

#### C4. Provider Survey

At baseline and follow-up, brief surveys will be administered to all participating physicians (n=80) by the NYU Study team to capture data on: satisfaction with workflow before and after intervention, information sources for EHR-CHW initiatives before and after intervention, acceptability of and satisfaction with the integrated EHR-CHW intervention, and barriers and facilitators of point-of-care use of the tools. The follow up provider survey will also include variables of organizational climate and priority and effects of the COVID-19 pandemic at the individual practices (eg. including questions to assess impact of COVID-19 on the practice and if providers are providing and/or tracking COVID-19 vaccination among patients in order to inform tailoring of remote intervention to support vaccination efforts and assist follow-up by CHWs to encourage vaccination among patients with diabetes who are at higher risk for complications from COVID-19)

The follow up survey will also include questions on cognitive impairment focused on use and knowledge of community resources for patients with cognitive impairment, as well as interest in information about referrals to resources and opportunities to provide feedback. These (See *Provider Survey*). Survey items with response scales will be designed to capture data on each of the research questions. For instance, participants may be asked to respond on a five-point scale from strongly agree to strongly disagree to the following statements: "Diabetes management recommendations are useful to me in my practice", or "The HbA1c testing alerts in the EHR are helpful to me", or to indicate how frequently they use each in a set of common information sources for clinical decision support. Provider Surveys will be administered via the online survey software, RedCap, or a paper copy if requested. Providers will be given the option of completing provider surveys electronically through a secure Redcap survey link. This data will be stored on New York University databases and will only be accessible through a unique secure link sent to an individual provider through RedCap's secure database by a NYU staff. Surveys will take approximately 15 minutes to complete.

#### C5. Key Informant Interviews

Qualitative key informant interviews will be conducted with physician champions at each clinic and/or administrator of each clinic, Healthfirst representatives, community advisory board members, research staff, and CHWs (n=100) (See *Key Informant Interview Guide*). At baseline, the interviews will be incorporated into the workflow analysis to assess current satisfaction and usage of EHR and health coaching. At follow-up, the interviews will assess barriers and facilitators to the implementation and adoption process of the integrated EHR-CHW intervention, fidelity to the interventions, and to solicit recommendations for the replication and scalability of the intervention to other sites and insurer organizations. Follow-up surveys completed during the pandemic will assess impact of COVID-19 on the practice, attitudes towards the remote CHW intervention adapted for their patients during the pandemic, and if providers are providing and/or tracking COVID-19 vaccination among patients. These questions

are intended to assess satisfaction with the remote intervention and inform strategies to support vaccination efforts and assist follow-up by CHWs to encourage vaccination among patients with diabetes who are at higher risk for complications from COVID-19 (See Key Informant *Interview Guide - provider – remote intervention*). The NYU Study team will conduct the interviews. Questions will be adapted from existing validated measures on acceptability, feasibility, adoption, organizational culture, and scalability. What organizational barriers and facilitators appear to influence implementation and how? Did members of the practice understand and respect the respective roles of physicians, CHWs, and other members of the team? How did this organization customize the intervention to better serve its own local needs? How were users involved in design and implementation? What are recommendations for replicating this model for other clinical settings and communities? Do project findings motivate payer organizations to reimburse CHW services? Key Informant Interviews will take approximately 30 minutes to complete.

## **II. CHARACTERISTICS OF THE RESEARCH POPULATION**

The overall number of subjects expected to participate in this study is 1066

This includes a total enrollment of 886 participants in the EHR-CHW Intervention (443 treatment participants and 443 wait-list control participants), 80 subjects who participate in the provider surveys and 100 participants in the key informant interviews.

### *CHW Intervention*

Inclusion Criteria: Participants will be eligible for study participation if they meet the following criteria: a) are of South Asian ethnicity; b) are at least 21 years of age and younger than age 75, c) had an appointment with a physician or mid-level clinician for routine non-emergent primary care in the last 12 months; d) a diagnosis of diabetes and e) an HbA1c reading of >7 in the last 12 months.

Exclusion Criteria: Patients under the age of 21 and older than 75 will be excluded. Pregnant women and all visits with an obstetrician gynecologist are excluded. Patients will be excluded if they were enrolled in a CHW led hypertension or diabetes education intervention in the past five years.

No children or vulnerable subjects will be enrolled in this study.

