### C. Study Design

#### C1. Overall Design/Clinic Selection/Clinic Enrollment

We will use a randomized controlled trial design with staggered-entry and a waitlisted control group to compare the effectiveness of an alert and registry-driven CHW-led coaching compared with usual care among patients with HbA1c at  $>7\%$ . Randomization will be at the individual-level and stratified by PCP, meaning eligible treatment and control participants will be randomized for each PCP. PCPs will be clustered into waves, aligning with the original stepped-wedge design. Entry into the study will be staggered in three waves, with each wave consisting of six to seven PCPs (See Figure 1). All 20 PCPs will be recruited and enrolled by month 6 of Year 1 (study period 6, Figure 1), and we will assign 6-7 practices into each of the 3 waves upon enrollment. For each PCP, there will be a total of two rounds of consecutive six-month CHW intervention periods for the treatment group: 1 month for recruitment and enrollment of treatment participants and five months of community health worker-led group education sessions (approximately one session per month). Data related to the study outcomes will be extracted from EHR systems a total four times (baseline, 6 month, 12 month, and 18 month) for each PCP; we will be comparing EHR data from 443 treatment participants with 443 control participants. Prior to allocation into treatment group, each treatment participant will be matched to a control participant based on age, gender, and BMI. Treatment participants will be split into two groups and assigned to either first or second round. All control participants will be waitlisted during the first round and will be offered the full CHW group education sessions during the second round as a point of service (i.e., not for research purposes).

Randomization at each PCP will occur during the first round. PCPs will be placed into waves based on geographic location and CHW caseload considerations. PCPs will be eligible for participation if they have a) an overall patient volume of  $N \geq 1000$  ; b) at least 70% of the patient population is South Asian; and c) the practice has used EHR for at least 12 months. All PCPs will sign a Memorandum of Understanding (MOU) between the PCP and NYU outlining study commitments.

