## B. Data Analysis and Data Monitoring

### B1. Aim 1 Analysis

AIM 1: Specific Aim I: Test the effectiveness of a multi-level diabetes management intervention compared to usual care. The primary outcome is reduction in HbA1c for patients with baseline HbA1c of >7%. The secondary outcomes include enhanced use of community and social services and increased self-efficacy.

*Hypothesis:* Individuals receiving the multi-level diabetes management intervention will be more likely to achieve >0.5% reduction in HbA1c 6 months following the index office visit than individuals receiving care as usual.

The analysis of the effect of intervention on the outcome measure will proceed using a Generalized Linear Mixed Model (GLMM). In particular, we will use a random effects model that assumes a binomial distribution with a logit link function. The comparison will make no linear assumption about the time trend for each outcome over the course of the trial. The model will be as follows:

$$(1) \quad \text{logit}(Y_{ijt}) = \mu + \alpha_j + \theta_t + \tau C_i,$$

where  $Y_{ijt} = 1$  if the  $i^{\text{th}}$  subject attached to the  $j^{\text{th}}$  clinic at time quarter  $t$  achieves an HbA1c reduction of 0.5% or more within six months following the index visit,  $Y_{ijt} = 0$  otherwise.  $\alpha_j$  is a random effect for clinic  $j$  with mean 0 and variance  $\sigma^2_b$ .  $\theta_t$  is a time-specific effect of quarter  $t, t \in (1, 2, \dots, 12)$ .  $C_i$  is an indicator variable, and  $C_i = 1$  if individual  $i$  receives care under the EHR/CHW intervention,  $C_i = 0$  if individual  $i$ .  $\tau$  represents the treatment effect of the intervention. The model will be fit using the LME4 package using R software. The hypothesis will be tested using two-sided level of significance  $\alpha = .05$ . Because outcome data will be derived from administrative data, we do not anticipate missing data. However, in the event that there is missing data, we will use multiple imputation under the assumption of data missing at random (MAR). This is consistent with following an intent-to-treat protocol. Sex as a biological variable will be addressed by exploring gender as a potential moderator of intervention effects.

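### Any HbA1c above 7 in the past year qualifies, the plan never says which reading is baseline, and the primary model does not adjust for baseline HbA1c

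*Combined protocol and SAP*

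**What the plan says.** - **Eligibility** (Section II, CHW Intervention, criterion (e)): the patient needs "an HbA1c reading of >7 in the last 12 months". Nothing requires this to be the latest reading.
- **Population of the primary outcome** (III.B1, and in similar words in I.A): "The primary outcome is reduction in HbA1c for patients with baseline HbA1c of >7" percent. Section I.C1 describes the comparison as "alert and registry-driven CHW-led coaching compared with usual care among patients with HbA1c at" more than 7%, without saying which reading counts.
- **Source list** (I.C2): "Generation of registry lists of individuals with A1C >7", again with no recency rule.
- **Endpoint** (III.B1): a subject is a responder who "achieves an HbA1c reduction of 0.5% or more within six months following the index visit". Neither the index visit nor the value from which the reduction is measured is defined.
- **Model (1)** (III.B1): besides the intercept there are three terms. One "is a random effect for clinic", one "is a time-specific effect of quarter", and the coefficient of the intervention indicator "represents the treatment effect of the intervention". Gender is mentioned separately as a possible moderator.
- **Allocation** (I.C1): treatment and control patients are matched on age, gender and BMI, and randomisation is stratified by PCP. HbA1c plays no part in either.
- **Data** (III.A2): HbA1c results with month and year are extracted for both arms.

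**The concern.** A patient at 8.0 ten months ago and 6.6 last month satisfies criterion (e). Whether that patient belongs to the population of the primary outcome depends on which value is called baseline, and the plan leaves this open.

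- If the latest value is baseline, patients at or below 7 can be in the trial, contrary to I.A and III.B1, and they have less room to fall by 0.5.
- If the qualifying value is baseline, the change starts from a reading up to 12 months old that was selected for being high. Falls before randomisation then count as responses.

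In either case the responder rate, and with it the power, depends on an undefined quantity. The starting value is likely to be a strong predictor of a 0.5-point fall, yet it is left out of the model, the matching and the stratification.

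**Working it through.** **1. The plan's sample size.** Inputs from the Power Calculation in III.B1: a 10-point difference in responders, two-sided 0.05, power above 80%, 15% loss, 886 patients at 1:1. The control rate is not stated. I assume 35% because it returns the plan's figure.

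n per arm = [1.960·√(2p̄(1−p̄)) + 0.842·√(p₁(1−p₁)+p₂(1−p₂))]² / (p₂−p₁)²

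With 0.35 v 0.45 and p̄ = 0.40: [1.960·√0.48 + 0.842·√0.475]² / 0.01 gives 376 after rounding up. Then 376/0.85 = 443 per arm, or 886 in total, an exact match. At 376 evaluable per arm, power is 0.888 for 20% v 30%, 0.821 for 30% v 40%, 0.800 for 35% v 45%, and at worst 0.784 for 45% v 55%. The stated power holds, or is missed by less than 2 points, but there is little slack.

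**2. Share of eligible patients whose latest value is 7 or lower.** This cannot be derived from the documents. Assumption: reading = T + e, with T normal between persons and e independent normal within persons. A patient is eligible if any of k readings in the year exceeds 7. The share is P(last reading ≤7, given any >7), from 400,000 simulated patients per scenario. With k = 1 it is 0 by construction.

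| Mean / between-person SD | Within-person SD | k = 2 | k = 4 |
|---|---|---|---|
| 8.0 / 1.5 | 0.4 | 6.0% | 9.9% |
| 8.0 / 1.5 | 0.8 | 11.2% | 17.3% |
| 7.5 / 1.2 | 0.4 | 9.1% | 15.0% |
| 7.5 / 1.2 | 0.8 | 15.8% | 24.5% |
| 7.2 / 1.0 | 0.4 | 12.8% | 20.6% |
| 7.2 / 1.0 | 0.8 | 20.5% | 30.9% |

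**3. Why the choice of baseline matters.** Simulations with mean 7.3 to 7.8, between-person SD 1.1, within-person SD 0.5 to 0.9 and 2 to 4 readings a year gave control responder rates of 20% to 38% measured from the latest reading. Measured from the highest qualifying reading they were 34% to 64%. The second is an outer bound; no section adopts it.

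**4. Adding baseline HbA1c to the logistic model.** Simulation with 376 per arm, no clinic or quarter effects, and 600 runs per scenario. Power without and with the term was 0.885 and 0.888, 0.898 and 0.923, 0.862 and 0.887. These are gains of 0.3, 2.5 and 2.5 points. A further simulation under other assumed distributions gave about 1 to 6 points, so the overall range is about 0 to 6.

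With no treatment effect the rejection rate was 0.065 without the term and 0.067 with it. The Monte Carlo standard error is √(0.05·0.95/600) = 0.009, so both lie within two standard errors of 0.05, and omission shows no inflation relative to adjustment.

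**5. Dilution, as an illustration only.** Let a share f be at or below 7, with 10% responders in both arms, and keep 35% v 45% for the rest. Control rate = (1−f)·0.35 + f·0.10; treatment rate = (1−f)·0.45 + f·0.10.
- f = 10%: 0.325 v 0.415, power 0.725.
- f = 20%: 0.300 v 0.380, power 0.639.
- If that group gains 5 points instead of 0: power 0.770 and 0.739.

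**6. What narrowing eligibility would cost.** Under the step 3 assumptions, requiring the latest value to exceed 7 removes about 8% to 25% of the eligible pool. If recruitment is limited by the pool, 376 × 0.92 = 346 and 376 × 0.75 = 282 evaluable per arm. At 35% v 45%, power falls from 0.800 to 0.767 and 0.680.

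**The case against.** The best defence is that this is a gap in definition and not a contradiction. If the qualifying reading is the baseline, everyone has a baseline above 7. If the phrase in III.B1 restricts the analysis, patients at or below 7 drop out of it. The alert and registry target uncontrolled diabetes, and eligibility is verified on a telephone screening form that is not in the text. The index visit and the scheduled baseline EHR extraction (I.C1) suggest a baseline near study start. Under individual randomisation a missing covariate costs precision, not validity, and tightening criterion (e) could cost more power than it returns.

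Most of this stands. It does not show that the plan is clear: the two readings of baseline give different responders, and the text does not choose between them. The precision argument also has a limit. Only treatment patients are phoned, screened and consented after assignment (I.C2; VI.A), whereas controls enter through EHR data without consent (VI.G, Control Participants). The groups actually analysed may therefore differ in baseline HbA1c despite randomisation.

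A reader might infer that pre-randomisation falls bias the comparison. They would be counted in both arms and do not by themselves do so.

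**Conclusion.** The point holds as a gap in definition and a missed covariate. Patients whose latest HbA1c is 7 or lower could enter, baseline is undefined, and model (1) does not adjust for it. The share affected is 0% with one reading a year and roughly 6% to 31% with two to four. The covariate is worth about 0 to 6 power points. Both ranges rest on assumed HbA1c distributions.

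Three stronger readings are tempting and not supported:
- **That patients at or below 7 do enter.** The documents give neither a count nor the number of readings per patient.
- **That power falls to about 73% to 64%.** This needs the planned 10-point difference to apply only above 7, with no effect below. The Power Calculation states the difference for treatment and control participants generally, so dilution may already be included. If the treatment shift is the same at every HbA1c level, requiring the latest value above 7 adds only about 1 to 3 points at an unchanged sample size. Section I.B5 reports larger reductions at the most elevated levels, so a larger loss is possible but not quantified.
- **That omitting the covariate inflates type I error.** Under randomisation it does not by itself.

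**What to change.** 1. Define baseline HbA1c as the most recent reading before randomisation, by the same rule in both arms, and say how it relates to the index visit. Because the extract gives only month and year, add a convention for readings in the month of randomisation, and make sure the baseline extraction reaches back far enough.
2. Add that value as a prespecified covariate in model (1).
3. Reconcile criterion (e) with I.A and III.B1, for example by a prespecified sensitivity analysis limited to patients whose baseline exceeds 7.
4. Treat a narrower criterion (e) as optional, and weigh it against the possible loss of 8% to 25% of the pool.

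Items 1 to 3 cost wording, one covariate and one extra analysis; HbA1c results are already extracted for both arms. The drawback is that the odds ratio becomes conditional on baseline HbA1c, so the report should say so.
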